6.1.5 Treatment duration

The planned duration of treatment is 24 weeks. Patients may be discontinued from treatment with the study drug earlier due to unacceptable toxicity or at the discretion of the investigator or the patient. Premature patient withdrawal refers to the point/time when the patient exits from the study prior to planned completion of all study treatment administration and/or

assessments. At this time, all study treatment is discontinued and after the 30-day safety follow-up (as possible), no further assessments are planned.

Patients may continue or resume prescribed iron chelation therapy as per investigator discretion.

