6.3.3 Follow-up for toxicities

Patients whose treatment is interrupted or permanently discontinued due to an adverse event or abnormal laboratory value must be followed for at least 30 days. All unresolved toxicities should be followed by the investigator until CTCAE Grade ≤ 1 , return to baseline, stabilization or the subject is lost to follow-up.

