7.1.7 Follow up for safety evaluations

All patients must have safety evaluations for 30 days after the last dose of study treatment. Data collected should be added to the Adverse Events, Prior and Concomitant Medications, and Surgical and Medical procedures eCRFs. All unresolved adverse events should be followed by the investigator until the events are resolved, or the subject is lost to follow-up.

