8.1 Adverse events

8.1.1 Definitions and reporting

An adverse event is defined as the appearance of (or worsening of any pre-existing) undesirable sign(s), symptom(s), or medical condition(s) that occur after patient's signed informed consent has been obtained.

Abnormal laboratory values or test results occurring after informed consent constitute adverse events only if they induce clinical signs or symptoms, are considered clinically significant, require therapy (e.g., hematologic abnormality that requires transfusion or hematological stem cell support), or require changes in study medication(s).

Adverse events that begin or worsen after informed consent should be recorded in the Adverse Events CRF. Conditions that were already present at the time of informed consent should be recorded in the Medical History page of the patient's CRF. Adverse event monitoring should be continued for at least 30 days following the last dose of study treatment. Adverse events (including lab abnormalities that constitute AEs) should be described using a diagnosis

whenever possible, rather than individual underlying signs and symptoms. When a clear diagnosis cannot be identified, each sign or symptom should be reported as a separate Adverse Event.

Adverse events will be assessed according to severity: mild, moderate or severe. Information about any deaths (related to an Adverse Event or not) will also be collected through a Death form.

The occurrence of adverse events should be sought by non-directive questioning of the patient (subject) during the screening process after signing informed consent and at each visit during the study. Adverse events also may be detected when they are volunteered by the patient (subject) during the screening process or between visits, or through physical examination, laboratory test, or other assessments. As far as possible, each adverse event should be evaluated to determine:

1. Severity (Mild, moderate or severe)
2. Its duration (Start and end dates)
3. Its relationship to the study treatment (Reasonable possibility that AE is related: No, Yes)
4. Action taken with respect to study or investigational treatment (none, dose adjusted, temporarily interrupted, permanently discontinued, unknown, not applicable)
5. Whether medication or therapy was given (no concomitant medication/non-drug therapy, concomitant medication/non-drug therapy)

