6. Whether it is serious, where a serious adverse event (SAE) is defined as in Section 8.2.1 and which seriousness criteria have been met
7. Outcome (not recovered/not resolved, recovered/resolved, recovering/resolving, recovered/resolved with sequelae, fatal, unknown).

If the event worsens the event should be reported a second time in the CRF noting the start date when the event worsens in toxicity. For moderate and severe events, if improvement to a lower grade is determined a new entry for this event should be reported in the CRF noting the start date when the event improved.

All adverse events should be treated appropriately. If a concomitant medication or non-drug therapy is given, this action should be recorded on the Adverse Event CRF.

Once an adverse event is detected, it should be followed until its resolution or until it is judged to be permanent, and assessment should be made at each visit (or more frequently, if necessary) of any changes in severity, the suspected relationship to the study treatment, the interventions required to treat it, and the outcome. Follow up will continue up to 30 days after study drug discontinuation.

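### Protocol 8.1.1 caps follow-up of an open adverse event at 30 days after stopping drug, against its own preceding sentence and Section 7.1.7 (minor)

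*Protocol*

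**What the plan says.** Section 8.1.1 of the protocol speaks three times about how long adverse events are watched.

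- On the collection window: "Adverse event monitoring should be continued for at least 30 days following the last dose of study treatment".
- On an event already found: "Once an adverse event is detected, it should be followed until its resolution or until it is judged to be permanent", with reassessment at each visit.
- As the closing sentence of that same paragraph: "Follow up will continue up to 30 days after study drug discontinuation".

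Section 7.1.7, which deals with safety follow-up, asks for 30 days of safety evaluation in every patient and then adds: "All unresolved adverse events should be followed by the investigator until the events are resolved, or the subject is lost to follow-up".

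Section 6.3.3 covers patients whose treatment was interrupted or stopped because of an adverse event or abnormal laboratory value. They "must be followed for at least 30 days", and open toxicities are then followed to a clinical end point, stabilization or loss to follow-up.

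**The concern.** The closing sentence of 8.1.1 sets a maximum where every neighbouring statement sets a minimum or an open-ended duty. A site holding an unresolved event on day 30 after the last dose can read 8.1.1 and stop, or read 7.1.7 and continue. Section 12 allows no authorized deviations, so the written instructions should be capable of being met together.

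What is at stake is clinical follow-up first and data second. The study was requested to characterize safety in children aged 2 to under 6. A child with, say, a non-serious mouth ulcer that did not affect dosing and had not healed by day 30 should stay under follow-up, yet one sentence gives the site wording to close the case. On the data side, Section 8.1.1 asks for the duration and outcome of each event. An event abandoned at day 30 would appear in the listings without an end date or final outcome, and SAP Section 5.1.2 does not impute adverse event end dates.

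**Working it through.** No formula or planned figure is involved, so the check is a comparison of every rule that could govern an event still open 30 days after the last dose.

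| Source | Applies to | Instruction at day 30 |
|---|---|---|
| Protocol 8.1.1, follow-up paragraph, first sentence | any detected event | continue until resolved or judged permanent |
| Protocol 8.1.1, follow-up paragraph, last sentence | same paragraph, same events | stop |
| Protocol 8.1.1, monitoring window | adverse event monitoring | 30 days is a minimum |
| Protocol 7.1.7 | all unresolved events | continue until resolved or lost to follow-up |
| Protocol 6.3.3 | events causing interruption or discontinuation | 30 days is a minimum; continue to a clinical end point, stabilization or loss |
| Protocol 8.1.2.1 | laboratory adverse events | continue until normal or explained |
| Protocol 6.3.3.1 | potential drug-induced liver injury | follow up and document the outcome |
| Protocol 8.2.2 | serious events | later developments reported whenever they occur |

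**Step 1: is there a conflict?** Yes. For one and the same open event, the first sentence of the paragraph and 7.1.7 say continue, and the last sentence says stop. Nothing in the protocol ranks 8.1.1 against 7.1.7.

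**Step 2: can the last sentence be read as the window for detecting new events?** Not naturally. That window is already set in 8.1.1, as a minimum. The sentence in question ends a paragraph that deals only with events already detected, and it is phrased as an upper limit.

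**Step 3: what would the cap do if applied literally?** An event starting 28 days after the last dose would be followed for at most 30 − 28 = 2 days.

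**Step 4: which events have no other protection?** Removing the laboratory, liver-injury, serious and 6.3.3 rows leaves mainly non-serious clinical events that did not lead to interruption or discontinuation.

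**Step 5: does any analysis change?**

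- The primary endpoint (SAP 2.8.1) counts patients with a selected gastrointestinal event. Protocol 10.5.3.2 restricts summaries to events starting or worsening on treatment, which by SAP 2.1.2.7 runs to 30 days after the last dose. What happens to an open event after day 30 adds or removes no patient, so the proportion and its Clopper-Pearson interval are unaffected.
- The adverse event tables listed in SAP 2.11.1 include none of duration or outcome.
- The outcome categories in 8.1.1 allow an event to be recorded truthfully as unresolved or resolving.

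The effect is therefore on the child's follow-up and on end date and outcome in the listings.

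**The case against.** The strongest reply is that the plan as a whole already answers the question. Section 7.1.7 sets out two tiers: 30 days of evaluation for everyone, then continued follow-up of whatever is still open. Section 6.3.3 and the monitoring sentence in 8.1.1 treat 30 days as a minimum. Protocol 10.5.3.1 and SAP 2.1.2.7 define a post-treatment period from day 31 and flag its data, so later data are expected. On this view, one loose sentence stands against several clear ones, and a site that stopped at day 30 would breach 7.1.7.

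Much of this stands. It shows what the authors most likely intended, and it is why the point is minor. It does not remove the contradiction, because the loose sentence sits in the section that defines adverse event reporting and nothing subordinates it.

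A reader might also infer that Section 6.1.5 repeats the cap, since it says that after premature withdrawal "after the 30-day safety follow-up (as possible), no further assessments are planned". The documents do not support that reading. The sentence concerns scheduled assessments and does not mention following open adverse events. Section 7.1.5 adds that stopping drug does not by itself make a child withdrawn from the study, so 6.1.5 covers only some of those who stop early.

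Nor would it be right to say that persistent gastrointestinal reactions are generally left uncovered. If drug was held or stopped for them, 6.3.3 applies and has no cap.

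**Conclusion.** The contradiction is real and rests on the text alone: 8.1.1 disagrees with itself and with 7.1.7 about when follow-up of an open adverse event ends. It matters as a safety instruction for young children, mainly for non-serious clinical events still open at day 30 that did not change dosing.

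Severity is minor. No planned estimate, interval or summary table moves. The documents give no share of events open at day 30, so the number of affected children cannot be calculated. Protocol 1.2.1.2 describes the common gastrointestinal and skin reactions as generally transient, which suggests few. Actual harm would also require a site to follow the last sentence of 8.1.1 in preference to 7.1.7.

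A reader might infer that the primary gastrointestinal proportion is biased or that serious events lose follow-up. Neither follows, given the endpoint's on-treatment window and the separate rules for serious events.

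**What to change.** Replace the last sentence of Protocol 8.1.1 with:

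> Follow-up will continue for at least 30 days after study drug discontinuation; adverse events unresolved at that time will be followed until resolved, judged permanent, or the subject is lost to follow-up (after withdrawal of consent, Section 7.1.6 applies).

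This keeps 30 days as a minimum, in line with the monitoring sentence in the same section. The reference to 7.1.6 is needed because that section restricts contact once consent is withdrawn.

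Add the judged-permanent end point to 7.1.7, which lacks it, so that the two sections match. Section 6.1.5 needs at most a cross-reference to 7.1.7. The SAP needs no change.

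The cost is one sentence in 8.1.1 and a few words in 7.1.7. Sites may have occasional contact after day 30, which 7.1.7 already requires. Adding the end point to 7.1.7 slightly reduces that duty, by letting follow-up close when an event is judged permanent, as 8.1.1 already allows.

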8.1.2 Laboratory test abnormalities

8.1.2.1 Definitions and reporting

Laboratory abnormalities that constitute an Adverse event in their own right (are considered clinically significant, induce clinical signs or symptoms, require concomitant therapy or require changes in study treatment), should be recorded on the Adverse Events CRF. Whenever possible, a diagnosis, rather than a symptom should be provided (e.g. anemia instead of low

hemoglobin). Laboratory abnormalities that meet the criteria for Adverse Events should be followed until they have returned to normal or an adequate explanation of the abnormality is found. When an abnormal laboratory or test result corresponds to a sign/symptom of an already reported adverse event, it is not necessary to separately record the lab/test result as an additional event.

Laboratory abnormalities, that do not meet the definition of an adverse event, should not be reported as adverse events. A severe event does not automatically indicate a SAE unless it meets the definition of serious as defined below and/or as per investigator's discretion. A dose hold or medication for the lab abnormality may be required by the protocol in which case the lab abnormality would still, by definition, be an adverse event and must be reported as such.

8.1.3 Adverse events of special interest

Adverse events of special interest (AESI) are defined as events (serious or non-serious) which are ones of scientific and medical concern specific to the sponsor's product or program, for which ongoing monitoring and rapid communication by the investigator to the sponsor may be appropriate. Such events may require further investigation in order to characterize and understand them.

Adverse events of special interest are defined on the basis of an ongoing review of the safety data. AESIs are discussed in detail in the Investigator Brochure.

Selected AEs, especially related to disturbances of the gastrointestinal tract, will be collected and assessed for severity: esophagitis, stomatitis, mouth ulceration, gastric ulcers, hemorrhage, abdominal pain, diarrhea, nausea, and vomiting.

8.2 Serious adverse events

8.2.1 Definitions

Serious adverse event (SAE) is defined as one of the following:

- Is fatal or life-threatening
- Results in persistent or significant disability/incapacity
- Constitutes a congenital anomaly/birth defect
- Is medically significant, i.e., defined as an event that jeopardizes the patient or may require medical or surgical intervention to prevent one of the outcomes listed above
- Requires inpatient hospitalization or prolongation of existing hospitalization,
- Note that hospitalizations for the following reasons should not be reported as serious adverse events:
 - Routine treatment or monitoring of the studied indication, not associated with any deterioration in condition
 - Elective or pre-planned treatment for a pre-existing condition that is unrelated to the indication under study and has not worsened since signing the informed consent
 - Social reasons and respite care in the absence of any deterioration in the patient's general condition

- Note that treatment on an emergency outpatient basis that does not result in hospital admission and involves an event not fulfilling any of the definitions of a SAE given above is not a serious adverse event.

8.2.2 Reporting

To ensure patient safety, every SAE, regardless of suspected causality, occurring after the patient has provided informed consent and until at least 30 days after the patient has stopped study treatment must be reported to Novartis within 24 hours of learning of its occurrence.

Any additional information for the SAE including complications, progression of the initial SAE, and recurrent episodes must be reported as follow-up to the original episode within 24 hours of the investigator receiving the follow-up information. An SAE occurring at a different time interval or otherwise considered completely unrelated to a previously reported one should be reported separately as a new event.

Any SAEs experienced after the 30 day safety evaluation follow-up period should only be reported to Novartis if the investigator suspects a causal relationship to the study treatment.

Information about all SAEs is collected and recorded on the Serious Adverse Event Report Form; all applicable sections of the form must be completed in order to provide a clinically thorough report. The investigator must assess and record the relationship of each SAE to each specific study treatment (if there is more than one study treatment), complete the SAE Report Form in English, and submit the completed form within 24 hours to Novartis. Detailed instructions regarding the SAE submission process and requirements for signatures are to be found in the investigator folder provided to each site.

Follow-up information is submitted in the same way as the original SAE Report. Each re-occurrence, complication, or progression of the original event should be reported as a follow-up to that event regardless of when it occurs. The follow-up information should describe whether the event has resolved or continues, if and how it was treated, whether the blind was broken or not, and whether the patient continued or withdrew from study participation.

If the SAE is not previously documented in the Investigator's Brochure or Package Insert (new occurrence) and is thought to be related to the Novartis study treatment, an oncology Novartis Chief Medical Office and Patient Safety (CMO&PS) department associate may urgently require further information from the investigator for Health Authority reporting. Novartis may need to issue an Investigator Notification (IN), to inform all investigators involved in any study with the same drug that this SAE has been reported. Suspected Unexpected Serious Adverse Reactions (SUSARs) will be collected and reported to the competent authorities and relevant ethics committees in accordance with Directive 2001/20/EC or as per national regulatory requirements in participating countries.

8.3 Emergency unblinding of treatment assignment

Not applicable

8.4 Pregnancies

Not applicable

8.5 Warnings and precautions

No evidence available at the time of the approval of this study protocol indicated that special warnings or precautions were appropriate, other than those noted in the provided Investigator Brochure. Additional safety information collected between IB updates will be communicated in the form of Investigator Notifications. This information will be included in the patient informed consent and should be discussed with the patient during the study as needed.

8.6 Data Monitoring Committee

Not applicable

8.7 Steering Committee

Not applicable

9 Data collection and management

9.1 Data confidentiality

Information about study subjects will be kept confidential and managed under the applicable laws and regulations. Those regulations require a signed subject authorization informing the subject of the following:

- What protected health information (PHI) will be collected from subjects in this study
- Who will have access to that information and why
- Who will use or disclose that information
- The rights of a research subject to revoke their authorization for use of their PHI.

In the event that a subject revokes authorization to collect or use PHI, the investigator, by regulation, retains the ability to use all information collected prior to the revocation of subject authorization. For subjects that have revoked authorization to collect or use PHI, attempts should be made to obtain permission to collect follow-up safety information (e.g. has the subject experienced any new or worsened AEs) at the end of their scheduled study period.

The data collection system for this study uses built-in security features to encrypt all data for transmission in both directions, preventing unauthorized access to confidential participant information. Access to the system will be controlled by a sequence of individually assigned user identification codes and passwords, made available only to authorized personnel who have completed prerequisite training.

Prior to entering key sensitive personally identifiable information (Subject Initials and exact Date of Birth), the system will prompt site to verify that this data is allowed to be collected. If the site indicates that country rules or ethics committee standards do not permit collection of these items, the system will not solicit Subject Initials. Exact date of birth will be solicited to establish that the subject satisfies protocol age requirements and to enable appropriate age-related normal ranges to be used in assessing laboratory test results.

9.2 Site monitoring

Before study initiation, at a site initiation visit or at an investigator's meeting, Novartis personnel (or designated CRO) will review the protocol and CRFs with the investigators and their staff. During the study, the field monitor will visit the site regularly to check the completeness of patient records, the accuracy of entries on the CRFs, the adherence to the protocol to Good Clinical Practice, the progress of enrollment, and to ensure that study treatment is being stored, dispensed, and accounted for according to specifications. Key study personnel must be available to assist the field monitor during these visits.

The investigator must maintain source documents for each patient in the study, consisting of case and visit notes (hospital or clinic medical records) containing demographic and medical information, laboratory data, electrocardiograms, audiology and ocular exams, and the results of any other tests or assessments. All information recorded on CRFs must be traceable to source documents in the patient's file. The investigator must also keep the original signed informed consent form (a signed copy is given to the patient).

The investigator must give the monitor access to all relevant source documents to confirm their consistency with the CRF entries. Novartis monitoring standards require full verification for the presence of informed consent, adherence to the inclusion/exclusion criteria and documentation of SAEs. Additional checks of the consistency of the source data with the CRFs are performed according to the study-specific monitoring plan.

9.3 Data collection

For sites using Electronic Data Capture (EDC), the designated investigator staff will enter the data required by the protocol into the Electronic Case Report Forms (eCRF). The eCRFs have been built using fully validated secure web-enabled software that conforms to 21 CFR Part 11 requirements, Investigator site staff will not be given access to the EDC system until they have been trained. Automatic validation programs check for data discrepancies in the eCRFs and, allow modification or verification of the entered data by the investigator staff.

The Principal Investigator is responsible for assuring that the data entered into eCRF is complete, accurate, and that entry and updates are performed in a timely manner.

